4.1.3 Compliance with Exercise Therapy

(1) Patients to be tabulated and analyzed

Safety Analysis Set

(2) Details to be tabulated and analyzed

For the status of compliance with exercise therapy, the frequency will be tabulated at each testing time point (at the start of Nesina treatment, 1 month, 3 months, 6 months, and 12 months after the start of Nesina treatment and last evaluation or treatment discontinuation). The latest datum will be used for last evaluation.

Total patients and patients who are taking concomitant insulin preparation, rapid-acting insulin secretagogues, SGLT-2 inhibitors, or other drugs will be tabulated.

Parameter	Category
Status of compliance	≥ 90%, ≥ 70%, ≥ 50%, < 50%, Not performed, or Unknown

Parameter	Category
with exercise therapy	

(3) Number of tables and figures

Table 4.1.3

5.0 Safety Tabulation and Analysis

5.1 Occurrence of adverse events and adverse drug reactions / infections

5.1.1 Occurrence of adverse events

(1) Patients to be tabulated and analyzed

Safety Analysis Set

(2) Details of tabulation and analysis

The following will be tabulated for adverse events.

Total patients and patients who are taking concomitant insulin preparation, rapid-acting insulin secretagogues, SGLT-2 inhibitors, or other drugs will be tabulated.

Parameter	Details of analysis
Number of patients with adverse events	Number of patients who experienced adverse events.
Number of adverse events	Number of adverse events. Count as an event if the same adverse event (LLT) occur multiple times in a patient. Count as different events for different LLTs even if they have the same PT.
Percent of patients with adverse events	Described in Section 1.1.
Type of adverse events	Will be broadly divided into the SOCs and tabulated by PT in the SOCs. In case of the laboratory test-related events, type of adverse events will be broadly divided into the SOCs and HLGTs for tabulation by PT. For the SOCs, the number of patients with adverse events and percent of patients with events will be described in the order of SOCs agreed internationally. For the PTs, the number of adverse events and percent of events will be described in the ascending order of PT codes. Count as an event if the same adverse event (LLT) occur multiple times in a patient. Count as different events for different LLTs even if they have the same PT.

(3) Number of tables and figures

Table 5.1.1-1

5.1.2 Occurrence of adverse drug reactions / infections

(1) Patients to be tabulated and analyzed

Safety Analysis Set

(2) Details of tabulation and analysis

The following will be tabulated for adverse drug reactions, etc. and serious adverse drug reactions, etc.

Total patients and patients who are taking concomitant insulin preparation, rapid-acting insulin secretagogues, SGLT-2 inhibitors, or other drugs will be tabulated.

Parameter	Details of tabulation and analysis
Number of patients with adverse drug reactions, etc.	Number of patients who experienced adverse drug reactions, etc.
Number of adverse drug reactions, etc.	Number of adverse drug reactions, etc. Count as an event if the same adverse drug reactions, etc. (LLT) occur multiple times in a patient. Count as different events for different LLTs even though they have the same PT.
Percent of patients with adverse drug reactions, etc.	Described in Section 1.1.
Type of adverse drug reactions, etc.	Will be broadly divided into the SOCs and tabulated by PT in the SOCs. In case of the laboratory test-related events, type of adverse events will be broadly divided into the SOCs and HLGTs for tabulation by PT. For the SOCs, the number of patients with adverse drug reactions, etc. and percent of patients with adverse drug reactions, etc. will be described in the order of SOCs agreed internationally. For the PTs, the number of adverse drug reactions, etc. and percent of adverse drug reactions, etc. will be described in the ascending order of PT codes. Count as an event if the same adverse drug reactions, etc. (LLT) occur multiple times in a patient. Count as different events for different LLTs even though they have the same PT.

(3) Number of tables and figures

Tables 5.1.2-1 and 5.1.2-2

5.1.3 Important Identified Risks, Important Potential Risks, and Important Missing Information

(1) Patients to be tabulated and analyzed

Safety Analysis Set

(2) Details of tabulation and analysis

The following will be tabulated for important identified risks, important potential risks, and important missing information (described in Section 1.2).

Total patients and patients who are taking concomitant insulin preparation, rapid-acting insulin secretagogues, SGLT-2 inhibitors, or other drugs will be tabulated.

Parameter	Details of tabulation and analysis
-----------	------------------------------------

Parameter	Details of tabulation and analysis
Number of patients with adverse events (or adverse drug reactions, etc.)	Number of patients who experienced adverse events (or adverse drug reactions, etc.) with important identified risks, important potential risks, and important missing information.
Number of adverse events (or adverse drug reactions, etc.)	Number of adverse events (or adverse drug reactions, etc.) with important identified risks, important potential risks, and important missing information. Count as an event if the same adverse event (or adverse drug reaction, etc.) (LLT) occur multiple times in a patient. Count as different events for different LLTs even if they have the same PT.
Percent of patients with adverse events (or adverse drug reactions, etc.)	Described in Section 1.1.
Type of adverse events (or adverse drug reactions, etc.)	Will be broadly divided into the important identified risks, important potential risks, and important missing information and tabulated by PT in them. For the PTs, the number of adverse events (or adverse drug reactions, etc.) and percent of adverse events (or adverse drug reactions, etc.) will be described in the ascending order of PT codes. Count as an event if the same adverse event (or adverse drug reaction, etc.) (LLT) occur multiple times in a patient. Count as different events for different LLTs even though they have the same PT.

(3) Number of tables and figures

Tables 5.1.3-1 and 5.1.3-2

5.2 Occurrence of Adverse Events and Adverse Drug Reactions / Infections in the Not Safety Analysis

Set

5.2.1 Occurrence of Adverse Events

(1) Patients to be tabulated and analyzed

Not Safety Analysis Set

(2) Details of tabulation and analysis

The following will be tabulated.

Total patients and patients who are taking concomitant insulin preparation, rapid-acting insulin secretagogues, SGLT-2 inhibitors, or other drugs will be tabulated.

Parameter	Details of tabulation and analysis
Number of patients with adverse events	Number of patients who experienced adverse events.
Number of adverse events	Number of adverse events. Count as an event if the same adverse event (LLT) occur multiple times in a patient. Count as different events for different LLTs even if they have the same PT.
Percent of patients with adverse events	Described in Section 1.1.
Type of adverse events	Will be broadly divided into the SOCs and tabulated by PT in the SOCs. In case of the laboratory test-related events, type of adverse events will be broadly divided into the SOCs and HLGTS for tabulation by PT. For the SOCs, the number of patients with adverse events and percent of patients with events will be described in the order of SOCs agreed internationally. For the PTs, the number of adverse events and percent of events will be described in the ascending order of PT codes. Count as an event if the same adverse event (LLT) occur multiple times in a patient. Count as different events for different LLTs even though they have the same PT.

(3) Number of tables and figures

Table 5.2-1

5.2.2 Occurrence of adverse drug reactions / infections

(1) Patients to be tabulated and analyzed

Not Safety Analysis Set

(2) Details of tabulation and analysis

The following will be tabulated.

Total patients and patients who are taking concomitant insulin preparation, rapid-acting insulin secretagogues, SGLT-2 inhibitors, or other drugs will be tabulated.

Parameter	Details of tabulation and analysis
Number of patients with adverse drug reactions, etc.	Number of patients who experienced adverse drug reactions, etc.
Number of adverse drug reactions, etc.	Number of adverse drug reactions, etc. Count as an event if the same adverse drug reactions, etc. (LLT) occur multiple times in a patient. Count as different events for different LLTs even if they have the

	same PT.
Percent of patients with adverse drug reactions, etc.	Described in Section 1.1.
Type of adverse drug reactions, etc.	
Will be broadly divided into the SOCs and tabulated by PT in the SOCs. In case of the laboratory test-related events, type of adverse events will be broadly divided into the SOCs and HLGTS for tabulation by PT.
 
For the SOCs, the number of patients with adverse drug reactions, etc. and percent of patients with adverse drug reactions, etc. will be described in the order of SOCs agreed internationally.
 
For the PTs, the number of adverse drug reactions, etc. and percent of adverse drug reactions, etc. will be described in the ascending order of PT codes. Count as an event if the same adverse drug reactions, etc. (LLT) occur multiple times in a patient. Count as different events for different LLTs even though they have the same PT.

(3) Number of tables and figures

Table 5.2-2

5.3 Occurrence of Adverse Drug Reactions / Infections by Severity, Onset Period, and Outcome

5.3.1 Occurrence of Adverse Drug Reactions / Infections by Severity, Onset Period, and Outcome

(1) Patients to be tabulated and analyzed

Safety Analysis Set

(2) Details of tabulation and analysis

Each parameter will be categorized by the categories described below to tabulate the type of adverse drug reactions, etc.

Total patients and patients who are taking concomitant insulin preparation, rapid-acting insulin secretagogues, SGLT-2 inhibitors, or other drugs will be tabulated.

Parameter	Category
Severity	Serious, Not serious, Not described
Onset period	1 to 14 days, 15 to 28 days, 29 to 84 days, 85 to 168 days, 169 to 336 days, 337days or Unknown
Outcome	Resolved, Resolving, Not resolved, Resolved with sequelae, Death, or Unknown

The method for tabulation of type adverse drug reactions, etc. is described below:

Parameter	Details of tabulation and analysis
Type of adverse drug	Will be broadly divided into the SOCs and tabulated by PT in the

Parameter	Details of tabulation and analysis
reactions, etc.	
SOCs. In case of the laboratory test-related events, type of adverse events will be broadly divided into the SOC and HLGs for tabulation by PT.
 
For the SOC, the number of patients with adverse drug reactions, etc. will be described in the order of SOC agreed internationally.
 
For the PTs, the number of adverse drug reactions, etc. will be described in the ascending order of PT codes. Count as an event if the same adverse drug reactions, etc. (LLT) occur multiple times in a patient. Count as different events for different LLTs even if they have the same PT. However, evaluate an event for the same LLT in accordance with the following order of priority:
 
Onset period: earlier event
 
Severity: Serious → Not serious → Not described
 
Outcome: Death → Resolved with Sequelae → Not resolved → Resolving → Resolved → Unknown

(3) Number of tables and figures

Tables 5.3-1 to 5.3-3

5.4 Patient Demographics and Frequency of Adverse Drug Reactions / Infections by Treatment

5.4.1 Patients demographics and Frequency of Adverse Drug Reactions / Infections by Treatment

(1) Patients to be tabulated and analyzed

Safety Analysis Set

(2) Details of tabulation and analysis

Each parameter will be categorized by the categories described below to tabulate the percent of patients with adverse drug reactions, etc.

The Fischer exact test will be used for parameters without rank data. The Mann-Whitney U test will be used for parameters with rank data. (The tests will be used for parameters with asterisk [*].)

Total patients and patients who are taking concomitant insulin preparation, rapid-acting insulin secretagogues, SGLT-2 inhibitors, or other drugs will be tabulated.

Parameter	Category
Sex*	Male, Female
Age*	< 65 years, ≥ 65 years
	< 75 years, ≥ 75 years
Concurrent liver disorder*	No, Yes
Severity of hepatic	Normal, Grades 1, 2, and 3, or Unknown

Parameter	Category
impairment*	
Concurrent renal disorder*	No, Yes
Severity of renal impairment* (eGFR)	Normal + Mild, Moderate + Severe, or Unknown
Severity of renal impairment* (serum creatinine)	Normal + Mild, Moderate + Severe, or Unknown
Concurrent heart disease*	No, Yes
Details of concurrent heart disease (overlapped)	Cardiac failure, myocardial infarction, or angina pectoris
Concurrent cardiac failure*	No, Yes
Severity classification of cardiac failure (NYHA classification)*	Classes NYHA I, NYHA II, NYHA III, and NYHA IV, or Unknown
Concurrent stroke-related disease*	No, Yes, or Unknown
Mean daily dose of Nesina	> 25 mg, 25 to >12.5 mg, 12.5 to > 6.25 mg, or ≤ 6.25 mg
Administration of concomitant medication (diabetic drug)	No, Yes
Concomitant medications (diabetic drugs) (overlapped)	α-glucosidase inhibitors, thiazolidines, sulfonylureas, biguanides, rapid-acting insulin secretagogues, or insulin preparations, DPP-4 inhibitors, GLP-1 receptor agonists, SGLT-2 inhibitors, combination of diabetic drugs, or other diabetic drugs
Administration of concomitant medication (protease drug)*	No, Yes, or Unknown
Administration of	No, Yes, or Unknown

Parameter	Category
concomitant medication (combined with renal excretory drug)*	

(3) Number of tables and figures

Table 5.4.1-1

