5.5 Occurrence of Adverse Drug Reactions / Infections by Age

(1) Patients to be tabulated and analyzed

Safety Analysis Set

(2) Details of tabulation and analysis

Age will be classified into < 65 years, ≥ 65 years and < 75 years, and ≥ 75 years for tabulation of type of adverse drug reactions, etc.

The method for tabulation of adverse drug reactions, etc. is same as that described in Section 5.1.

Total patients and patients who are taking concomitant insulin preparation, rapid-acting insulin secretagogues, SGLT-2 inhibitors, or other drugs will be tabulated.

(3) Number of tables and figures

Tables 5.5-1 to 5.5-2

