5.7 Occurrence of Adverse Drug Reactions / Infections by Liver Disorder

(1) Patients to be tabulated and analyzed

Safety Analysis Set

(2) Details of tabulation and analysis

Concurrent liver disorder will be classified into yes or no for tabulation of type of adverse drug reactions, etc.

The method for tabulation of adverse drug reactions, etc. is same as that described in Section 5.1.

Total patients and patients who are taking concomitant insulin preparation, rapid-acting insulin secretagogues, SGLT-2 inhibitors, or other drugs will be tabulated.

- (3) Number of tables and figures

Table 5.7-1

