5.8 Occurrence of Adverse Drug Reactions / Infections by Liver Impairment

- (1) Patients to be tabulated and analyzed

Safety Analysis Set

- (2) Details of tabulation and analysis

Severity of liver impairment will be classified into Grade 1, 2, or 3 or unknown for tabulation of type of adverse drug reactions, etc.

The method for tabulation of adverse drug reactions, etc. is same as that described in Section 5.1.

Total patients and patients who are taking concomitant insulin preparation, rapid-acting insulin secretagogues, SGLT-2 inhibitors, or other drugs will be tabulated.

- (3) Number of tables and figures

Table 5.8-1

5.9 Occurrence of Adverse Drug Reactions / Infections by Presence of Concurrent Renal Disorder

- (1) Patients to be tabulated and analyzed

Safety Analysis Set

- (2) Details of tabulation and analysis

Concurrent renal disorder will be classified into yes or no for tabulation of type of adverse drug reactions, etc.

The method for tabulation of adverse drug reactions, etc. is same as that described in Section 5.1.

Total patients and patients who are taking concomitant insulin preparation, rapid-acting insulin secretagogues, SGLT-2 inhibitors, or other drugs will be tabulated.

- (3) Number of tables and figures

Table 5.9-1

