5.10 Occurrence of Adverse Drug Reactions / Infections by Severity of Renal Impairment

- (4) Patients to be tabulated and analyzed

Safety Analysis Set

(5) Details of tabulation and analysis

Severity of renal impairment will be classified into normal + mild, moderate + severe, or unknown, according to the criteria for the severity of renal impairment (eGFR and serum creatinine) for tabulation of type of adverse drug reactions, etc.

The method for tabulation of adverse drug reactions, etc. is same as that described in Section 5.1.

Total patients and patients who are taking concomitant insulin preparation, rapid-acting insulin secretagogues, SGLT-2 inhibitors, or other drugs will be tabulated.

(6) Number of tables and figures

Tables 5.10-1 and 5.10-2

5.11 Occurrence of Adverse Drug Reactions / Infections by Presence of Concurrent Heart Disease

(1) Patients to be tabulated and analyzed

Safety Analysis Set

(2) Details of tabulation and analysis

Concurrent heart disease will be classified into yes or no for tabulation of type of adverse drug reactions, etc.

The method for tabulation of adverse drug reactions, etc. is same as that described in Section 5.1.

Total patients and patients who are taking concomitant insulin preparation, rapid-acting insulin secretagogues, SGLT-2 inhibitors, or other drugs will be tabulated.

(3) Number of tables and figures

Table 5.11-1

5.12 Occurrence of Adverse Drug Reactions / Infections by Presence of Concurrent Heart Failure

(1) Patients to be tabulated and analyzed

Safety Analysis Set

(2) Details of tabulation and analysis

Concurrent heart failure will be classified into yes or no for tabulation of type of adverse drug reactions, etc.

The method for tabulation of adverse drug reactions, etc. is same as that described in Section 5.1.

Total patients and patients who are taking concomitant insulin preparation, rapid-acting insulin secretagogues, SGLT-2 inhibitors, or other drugs will be tabulated.

(3) Number of tables and figures

Table 5.12-1

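### The age, hepatic and renal safety tables cover adverse drug reactions only, so any-cause hypoglycaemia is never shown by stratum: a cheap improvement, not a breach

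*SAP*

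**What the plan says.** Protocol 10.6 says that safety and efficacy will be stratified for elderly patients and for those with hepatic or renal impairment; it names no safety measure. Protocol 10.4.2, on factors affecting safety, names adverse drug reactions (ADRs).

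The SAP follows 10.4.2:

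- 5.4.1: "Each parameter will be categorized by the categories described below to tabulate the percent of patients with adverse drug reactions, etc".
- 5.7: "Concurrent liver disorder will be classified into yes or no for tabulation of type of adverse drug reactions, etc".
- 5.8: "Severity of liver impairment will be classified into Grade 1, 2, or 3 or unknown for tabulation of type of adverse drug reactions, etc".
- 5.9: "Concurrent renal disorder will be classified into yes or no for tabulation of type of adverse drug reactions, etc".
- 5.10: "Severity of renal impairment will be classified into normal + mild, moderate + severe, or unknown", again for types of ADR.
- 5.5 does the same for age.

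Sections 5.5 and 5.7 to 5.10 all carry the sentence "The method for tabulation of adverse drug reactions, etc. is same as that described in Section 5.1". This imports the 5.1 counting method for ADRs and leaves the adverse-event half of 5.1 behind.

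SAP 1.2 defines hypoglycaemia by a list of ten preferred terms among adverse events, whatever the causality. The section that uses this definition is 5.1.3, which reports "Number of patients who experienced adverse events (or adverse drug reactions, etc.) with important identified risks, important potential risks, and important missing information". Its only breakdown is total and partner-drug group. The other any-cause tables (5.1.1, and 5.2.1 for patients outside the safety set) have the same breakdown.

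**The concern.** By design the survey enrols patients already on insulin, a rapid-acting secretagogue or a similar agent, so a competing explanation for hypoglycaemia is always present. Protocol Table 3 permits Not related when the event is presumed to come from a concomitant drug. An episode graded that way drops out of every table by age, liver or kidney status.

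That would not matter if attribution were the same in every stratum. If investigators blamed insulin more readily in, say, renal patients, the ADR tables could hide a real difference or create a false one. A reader of the planned output could not tell, because no any-cause count stands beside the ADR count. Protocol 3.2 presents the 1,000 patients as supplying about 600 elderly, 150 renal and 100 hepatic patients, so these strata are part of the survey's stated rationale.

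**Working it through.** **Text check.** Of the SAP safety event tables, any-cause events appear in 5.1.1, 5.1.3 and 5.2.1 only. Age, hepatic and renal strata appear in 5.4.1, 5.5 and 5.7 to 5.10 only, all for ADRs. The two sets do not overlap.

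**Stratum shares.** Protocol 3.2 gives 58.0% elderly, 15.1% renal and 13.3% hepatic. Applied to 1,000, these give 580 (stated as about 600), 151 (about 150) and 133 (about 100). The hepatic rounding is loose, so I use the percentages.

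**What 5.1.3 could rule out.** The documents give no hypoglycaemia rate and no attribution share, so only limits can be worked out.

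- S: overall share of hypoglycaemia patients counted as ADR. It is readable from 5.1.3 if patient counts are given for each risk item. I assume 95% and 80%.
- p: the stratum's share of patients (Protocol 3.2).
- R: true all-cause risk ratio, stratum against the rest. I assume 1 and 2.
- f: the stratum's share of hypoglycaemia patients, f = pR / (pR + 1 − p).

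The ADR risk ratio divided by R equals the attribution share inside the stratum divided by the share outside it.

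- Lower limit, with as many non-ADR patients as possible inside the stratum: 1 − (1 − S)/f, not below 0.
- Upper limit, with none inside: 1 / (1 − (1 − S)/(1 − f)).

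At R = 1, f = p. At R = 2:

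- elderly f = 1.16/1.58 = 0.734
- renal f = 0.302/1.151 = 0.262
- hepatic f = 0.266/1.133 = 0.235

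| Stratum | S = 95%, R = 1 | S = 95%, R = 2 | S = 80%, R = 1 | S = 80%, R = 2 |
|---|---|---|---|---|
| Elderly | 0.91–1.14 | 0.93–1.23 | 0.66–1.91 | 0.73–4.04 |
| Renal | 0.67–1.06 | 0.81–1.07 | 0–1.31 | 0.24–1.37 |
| Hepatic | 0.62–1.06 | 0.79–1.07 | 0–1.30 | 0.15–1.35 |

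Example: renal, S = 95%, R = 2 gives 1 − 0.05/0.262 = 0.81, so a true ratio of 2 could appear as low as about 1.6.

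**Illustration of the mechanism (all rates assumed).** Take any-cause hypoglycaemia of 10% in 580 elderly and 5% in 420 others, a ratio of 2. If 40% of the elderly cases and 80% of the others are graded as ADR, the ADR rates are 10% × 0.4 = 4.0% and 5% × 0.8 = 4.0%, a ratio of 1. Overall S would be (23.2 + 16.8)/(58 + 21) = 51%. Table 5.1.3 would show that figure, but not which stratum it came from.

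**Precision of an any-cause row (Clopper-Pearson 95% CI, counts assumed).** 5/100: 1.6–11.3%. 7/133: 2.1–10.5%. 8/150: 2.3–10.2%. 30/600: 3.4–7.1%.

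**The case against.** The strongest reply is that nothing has gone wrong. Protocol 10.4.2 names ADRs, 10.6 names no measure, and the SAP supplies one. A reader might infer from the word safety in 10.6 that an any-cause table was promised and omitted; the text does not go that far. This stands, and it is why the point is an optional improvement.

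Second, Table 3 leans towards a high S. Temporal correlation alone supports Related, mixed causation is also Related, and Protocol 9.2.6 requires a recorded rationale for Not related. Table 5.1.3 also shows attribution by partner drug, the most relevant axis for the proposed mechanism. This stands in part. It makes a large distortion less likely, but the table above shows that even S = 95% leaves room in the two smaller strata.

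Third, those limits rest on few patients. At an assumed 5% rate in 1,000 there are 50 hypoglycaemia patients, and S = 95% leaves 2.5 not counted as ADR. The renal limit at R = 1 needs all of them among about 7.5 renal cases. That is fair: these are worst cases, smaller than the sampling error of the rates.

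Fourth, the printed ADR definition in SAP 1.1 takes events assessed as Not related, which looks inverted. I read it as every event other than Not related. Read literally, the stratum tables would show the opposite causality subset. On either reading they show one subset and never the total.

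Fifth, the event terms, causality, age, AST/ALT and creatinine are all collected, and Protocol 14.2 allows data to be investigated if a safety question arises. So the gap is in the planned tables, not in the data. Choosing hypoglycaemia over the other risks in SAP 1.2 is a judgement; I make it because the partner drugs supply a ready alternative cause.

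**Conclusion.** The point holds as a cheap improvement. The planned tables cannot show whether attribution of hypoglycaemia differs by age, hepatic or renal status, because the any-cause count is missing from every stratum table. No commitment is broken.

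The size is unknown. A reader might infer that attribution does differ between strata; no rate or share in the documents supports that. A reader might also take the 0.67 and 0.62 limits to mean that a true renal or hepatic excess could be understated by about a third when S is 95%. Those limits belong to a true ratio of 1, where there is no excess. With a true two-fold excess the limits are 0.81 and 0.79, about a fifth. At S = 80% and a true ratio of 2 they fall to 0.24 and 0.15. All are worst-case limits resting on assumed S and R and on the Protocol 3.2 shares. For the elderly, S near 95% would nearly settle the question if the all-cause ratio is near 1 (0.91–1.14).

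**What to change.** In Tables 5.5-1, 5.5-2, 5.7-1, 5.8-1, 5.9-1, 5.10-1 and 5.10-2, for total patients, add two descriptive rows using the SAP 1.2 hypoglycaemia definition:

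- patients with at least one hypoglycaemia event of any causality;
- patients with at least one hypoglycaemia ADR.

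Give each as n/N and %, and state that N is the number of patients in the stratum, because the percentage formula in SAP 1.1 uses the whole Safety Analysis Set. No test. Both rows are needed: the existing preferred-term rows count events and count different lowest-level terms separately, so they would not give a clean share against a patient count.

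In 5.8, include the Normal category already listed in 5.4.1 ("Normal, Grades 1, 2, and 3, or Unknown"), so that the grades have a comparator. Leave 5.4.1 unchanged; its strata are largely the same.

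Cost: SAP wording and two rows in seven existing tables, 19 strata counting Normal and Unknown (2 + 2 + 2 + 5 + 2 + 3 + 3). No new data or coding. The rows include background risk with no control arm, and small strata are imprecise (5/100: 1.6–11.3%). Splitting further by partner drug would often be too sparse to read: 25 hepatic patients per group (100 over four groups, assumption) at 3% (assumption) give 0.75 expected cases and a 0.97^25 = 47% chance of none. That is why the rows are proposed for total patients only.
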